#### 8. RESEARCH METHODS

#### 8.1. Study Design

A prospective cohort study using data from individual medical records from participating clinical sites will be conducted to meet the study objectives.

For this non-interventional study, treatment decisions will be made by the treating physician according to standard practice, taking into account the treatment history, individual clinical characteristics, the approved SmPC for CAB and RPV oral and LA formulations and for the contemporary regimen and local guidelines or recommendations. Only clinical sites whose standard of care guidance includes HIV subtype testing and resistance testing among individuals with virologic failure will be include in the study to ensure collecting resistance data. Resistance and subtype testing (if not already done) will also be part of the routine clinical care, required of the clinical sites, so the individuals who discontinue the regimen and have virological failure during the 48 month period after discontinuation will have the requisite resistance testing data.

#### 8.2. Study Population and Setting

#### 8.2.1. Study Setting

Potential NEAT ID investigational sites across Europe will be contacted for feasibility and resistance testing practices as part of their SoC. Clinical sites with resistance testing following virologic failure as part of SoC and the ability to perform the tests will be selected to participate in this study. Follow-up period will start from the date of starting the treatment regimen after approval and commercial availability of the regimen.

NEAT ID Network team will perform site monitoring activities to assess protocol issues, consent, data quality and Study Management quality performance.

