#### 6. RATIONALE AND BACKGROUND

#### 6.1. Background

Cabotegravir (CAB), a human immunodeficiency virus type-1 (HIV-1) integrase strand transfer inhibitor (INSTI), in combination with Rilpivirine (RPV), an HIV-1 non-nucleoside reverse transcriptase inhibitor (NNRTI), is indicated as a complete regimen for the treatment of Human Immunodeficiency Virus type 1 (HIV-1) infection in adults who are virologically suppressed (HIV-1 RNA <50 copies/mL) on a stable antiretroviral (ARV) regimen without present or past evidence of viral resistance to, and no prior virological failure with agents of the NNRTI and INI class. Prior to the initiation of CAB long acting (LA) injection, CAB tablets together with RPV tablets should be taken for approximately one month (at least 28 days) to assess tolerability to CAB and RPV.

Treatment with CAB+RPV LA should be prescribed by a physician experienced in the management of HIV infection. Each injection should be administered by a healthcare provider (HCP). Prior to starting the regimen, the HCP should carefully select PLWH who agree to the required injection schedule and counsel individuals about the importance of adherence to scheduled dosing visits to help maintain viral suppression and reduce the risk of viral rebound and potential development of resistance associated with missed doses. Following discontinuation of CAB in combination with RPV injection, it is essential to adopt an alternative, fully suppressive ARV regimen per the summary of product characterization (SmPC).

The Marketing Authorization Holder (MAH) proposes a prospective cohort study to monitor for clinical effectiveness, discontinuation and resistance among PLWH receiving CAB+RPV LA in routine clinical practice. The proposed multi-site study "Real-world evidence for effectiveness of Two Drug Regimen, Antiretroviral therapy with integrase inhibitors plus a reverse transcriptase inhibitor Drug (COMBINE-2)" for the CAB+RPV LA regimen will be conducted through collaboration with NEAT ID Network, a well-established network of clinical sites across Europe.

The study will not require any changes to the standard of care that PLWH receive, and decisions on ARV treatment are made by the healthcare providers taking into account the treatment history, individual clinical characteristics and local guideline or recommendations. A detailed study protocol, once approved by EMA, will be implemented by the NEAT ID Network team.

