#### 8.5. Data Collection

Following the approval of CAB LA and RPV LA, the study will collect follow up data prospectively on 1000 PLWH treated with the CAB+RPV LA regimen, for a follow-up period of 24 months. Participants who discontinue CAB+RPV LA regimen will be followed up for 48 months after switching to another ARV regimen. The NEAT ID Network coordinating center will receive data from the clinical sites per the protocol for the study. Detailed data collection form will be used to collect comprehensive data from clinical sites including dates of injections, clinical and laboratory parameters (virologic, immunologic, biochemistry, haematology and pathology), documented history of resistance at regimen initiation, resistance and HIV subtype data at virologic failure and after discontinuation and switching to another ARV regimen. Only clinical sites that, as SoC test all participants at virologic failure, for resistance and HIV subtype data and after discontinuation and switching to another ARV regimen will be included in the study.

In order to maintain confidentiality, the subject will be identified only by subject number. Subject data will be collected via extraction from individual medical record as source data by appropriately trained and authorised member(s) of the study team who must be identified and authorised in writing by the Principal Investigator (PI). A delegation of responsibility log will be updated accordingly.

Sites will provide / upload data every 6 months to the data management team who will store the data on a secure database with access to authorised personnel of the study management team only, maintained the log of authorised personnel by the sponsor representative.

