# AIM 3. Assess the clinical effectiveness among PLWH who initiate CAB+RPV LA regimen

Given that this study involves PLWH in routine clinical care, and who may not attend clinic appointments at 6, 12 or 24 months, a window of 12 weeks around the date in question will be used for virologic failure. Thus, the proportion with virologic failure during first six months, at 6, 12 or 24 months  $\pm$  6 weeks will be used; and if none is available, the first measurement during first six months, after 6, 12 or 24 months (and at most 6 weeks after the measurement).

Proportion of participants who continue to be suppressed (VL of <50 copies/mL) at each time point (after 6, 12 and 24 months of follow up) will be estimated, as well as proportion of individuals with VL of <200 copies/mL. CD4 counts will also be assessed. The proportion of participants with virologic failure (2 consecutive HIV RNA VL  $\geq$ 200 copies/mL or one HIV RNA VL level  $\geq$ 200 copies/mL followed by a discontinuation of CAB+RPV LA regimen) will be estimated and time to failure will be assessed by the Kaplan-Meier method. The two-sided 95% associated confidence interval will be calculated with Kalbfleisch and Prentice's formula. Time to event will be defined as the time between the date of the initiation of CAB+RPV LA regimen and the date of virologic failure. Follow-up will be censored at the analysis time point, or the date of last study contact, or date of discontinuation of CAB+RPV LA regimen, or the date of lost to follow-up, whichever will occur first.

Genotypic resistance testing will be performed in participants with confirmed HIV RNA VL  $\geq$ 200 copies/mL. Resistance interpretation will be given using the Stanford algorithm (https://hivdb.stanford.edu/hivdb/by-mutations). All drug resistance mutations identified will be described and number and percentage indicated. The proportion of participants with genotypic resistance viruses among those with virological failure will be estimated by the number of participants with genotypic resistance viruses divided by the total number of participants with virological failure. The associated two-sided 95% exact (Clopper–Pearson) confidence intervals will be calculated. The frequency of viral subtype among those with virologic failure will be reported.

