#### $eForm\ Code: RESTST\ eForm\ Title: Resistance\ Testing\ -\ Annotations\ Table$

ID	CODE	NAME	EXP.CODE	TYPE	FMT/LEN	DERIVATION	CAT. VALUES					
1	_	Subject ID	ZORNID_D	Text	10	R2T:DEMOC:20R1ID						
2	RESYN	Resistance test carried out?	RESYN	Category	3		N=No Y=Yes					
Repea	Repeating Question Group: , Borders: Yes, RowStatus: Yes, RowStatus: Yes, RowNumbers: Yes,											
3	RESDAT	Date of resistance testing	KESDA I	Date/Time	aa/mm/yyyy							
4	RESAVAIL	Is test report available?	RESAVAIL	Category	3		N=No Y=Yes					
5	RESIDENT	Was new resistance identified?	RESIDENT	Category	3		N=No Y=Yes					
6	RESCLASS	Class of ARV Drug	RESCLASS	Category	19		1=Protease/PI Z=NNK I I 3=NKI I/NtKI I 4=Integrase inhibitor 5=Other					
7	RESSPEC	ARV Drug Name - 1 per row	RESSPEC	Text	100							
8	RESMUT	List each mutation	RESMUT	Text	100							
9	SORAIN	Is subtype data available?	SORAN	Category	3		N=No Y=Yes					
10	HIAZOR	HIV Subtype	HIAZOR	Category	5		1=HIV-1 Z=HIV-Z					
11	HIAZORCA	HIV Subtype Group (If known)	HIAZORCA	Text	50							
Repea	ting Question Group: , Bor	ders: Yes, RowStatus: Yes, RowN	umbers: Yes, DisplayRe	ows: 3, InitialRows	1, Min Repeats: 1	, Max Repeats: 20, Main Row Type: Single-Line, Sub Row Type: Multi-Line						
12	CRREAS	Data Keview Keason	CRREAS	Category	36, Optional		See Appendix					
			CRDAT		·							
12	CKDAT	Review Date	CKDAT	Date/Time	dd/mm/yyyy, Optional							
14	CRNOT	Notes for Next Review	CRNOT	Text	500, Optional							

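### The resistance form does not record whether integrase and reverse transcriptase were each sequenced with a result, so an unread integrase is coded like wild type and can only pull reported resistance down

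*Protocol*

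**What the plan says.** Three statements in the Protocol govern which sites may take part. Section 8.2.1: "Clinical sites with resistance testing following virologic failure as part of SoC and the ability to perform the tests will be selected". Section 8.1: "Only clinical sites whose standard of care guidance includes HIV subtype testing and resistance testing among individuals with virologic failure". Section 8.5: "Only clinical sites that, as SoC test all participants at virologic failure, for resistance and HIV subtype data". None names a gene region or drug class. Section 8.3.2 refers only to resistance testing with subtype.

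Section 8.7, AIM 3, states "Genotypic resistance testing will be performed in participants with confirmed HIV RNA VL" at or above 200 copies/mL, with interpretation by the Stanford algorithm. The resistance proportion counts participants with genotypically resistant virus, "divided by the total number of participants with virological failure", with a Clopper-Pearson interval. AIM 3 adds: "All drug resistance mutations identified will be described and number and percentage indicated". It gives no denominator for those percentages.

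The Resistance Testing form in Annex 1 has fields for test done, test date, report available, one yes/no item ("Was new resistance identified"), drug class (integrase inhibitor and NNRTI are among the options), drug name, mutation and subtype. The same form is used for earlier tests, for failures on the regimen and for failures in the 48 months after a switch.

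**The concern.** Section 6.1 describes cabotegravir as an integrase inhibitor and rilpivirine as an NNRTI. Resistance to the first is read from integrase and resistance to the second from reverse transcriptase. A test that covers one region and not the other is a valid resistance test under the site rules but answers only half of the question.

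The form cannot show this. Resistance that is found can be entered under its class, so positive results are safe. The gap lies in the negatives. An entry of no new resistance, or of new resistance with an NNRTI row only, looks the same whether integrase was wild type, failed to amplify or was never requested. The same holds for reverse transcriptase the other way round.

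Resistance monitoring is objective 4, and only 20 to 60 failures are expected, so a few unread tests could shift the result. A later analysis plan can choose its denominator only from variables that were collected. This point concerns failures that were tested, but not for the relevant region. Failures with no test at all are a separate matter.

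**Working it through.** **Inputs from Protocol section 8.4.** Number of failures to be genotyped: n = 20 to 60. Assumed resistance among failures: 50%, any class.

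**Inputs not in the documents (assumptions).**
- q, the share of failure genotypes without an integrase result: 10%, 20% or 30%.
- True INSTI resistance among failures: 50%. This borrows the any-class rate.
- s, the share of resistant viruses whose only resistance mutations are in integrase.
- Whether integrase was read does not depend on whether the virus is resistant.

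**Step 1: the plan's own figures.** Clopper-Pearson limits for 50% are 0.272 to 0.728 at n = 20, 0.338 to 0.662 at n = 40 and 0.368 to 0.632 at n = 60. These agree with Table 4 to two decimals (0.27–0.73, 0.34–0.66, 0.37–0.63).

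**Step 2: INSTI resistance over all failures.** If an unread integrase falls among the non-resistant, the expected reported proportion is 0.50 × (1 − q):
- q = 10%: 0.50 × 0.9 = 45%
- q = 20%: 0.50 × 0.8 = 40%
- q = 30%: 0.50 × 0.7 = 35%

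**Step 3: would the interval reveal or hide the shift?** Exact 95% intervals at the expected counts:

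| n | q = 10% | q = 20% | q = 30% |
|---|---|---|---|
| 20 | 9/20: 23.1–68.5% | 8/20: 19.1–63.9% | 7/20: 15.4–59.2% |
| 40 | 18/40: 29.3–61.5% | 16/40: 24.9–56.7% | 14/40: 20.6–51.7% |
| 60 | 27/60: 32.1–58.4% | 24/60: 27.6–53.5% | 21/60: 23.1–48.4% |

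Eight of the nine intervals include 50%. Only n = 60 with q = 30% excludes it.

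**Step 4: denominator limited to successful integrase reads.** At n = 60 and q = 30%, 60 × 0.7 = 42 tests are readable: 21/42 = 50% (34.2–65.8%). At n = 20 and q = 30%, 20 × 0.7 = 14 are readable: 7/14 = 50% (23.0–77.0%). The estimate is restored and the interval is wider.

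**Step 5: the any-class proportion that AIM 3 defines.** A virus with a detected NNRTI mutation still counts as resistant, so only integrase-only resistance is lost: 0.50 × (1 − s × q). At s = 0.25 and q = 0.3 this is 0.50 × 0.925 = 46.3%. At s = 0.5 and q = 0.3 it is 0.50 × 0.85 = 42.5%.

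**The case against.** **No site is shown to omit integrase.** Section 8.2.1 says sites will be asked about their resistance testing practices, and the feasibility questionnaire is not at hand. The question may already be asked. This stands: q could be zero. But feasibility answers describe a site's routine, not the result of a particular test, so a failed integrase read would still go unrecorded.

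**No INSTI-specific proportion is defined.** AIM 3 fixes only the any-class proportion, and the mutation percentages have no stated denominator. A reader might infer that the plan explicitly scores every unread integrase as INSTI-negative in a named endpoint. It does not; the class-specific figures above show what an all-failures denominator would give. For the any-class proportion the denominator is fixed, and an integrase-only resistant virus without an integrase read would be counted as non-resistant.

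**The interval that misses 50% is a corner case.** A reader might take 21/60 as typical. It needs the top of the 2% to 6% failure range in section 8.4 and the highest assumed q. The trial cited there had 1.6% failure at week 48, under a different threshold.

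**Reports can be retrieved.** The form records whether a report is available, the Source Data Upload form accepts de-identified documents at a monitor's request, and section 8.6.1 provides for continuing review and queries. It would therefore be wrong to infer that the gap could never be detected or corrected. With 20 to 60 failures, retrieval is feasible. Still, nothing directs genotype reports to that form, and retrieval yields no coded variable.

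**Completion guidelines are not shown.** The class and mutation fields are not marked optional, so sites might enter a class beside a negative result. No instruction on the form gives such an entry the meaning of a region read and found negative.

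**Conclusion.** The point holds as a gap in data capture with a known direction and an unknown size. The form cannot separate integrase unread from integrase wild type, the site rules do not close the gap, and AIM 3 divides by all failures. Provided that resistance found is recorded correctly, missing reads can only lower reported INSTI resistance, and any-class resistance by less.

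Under assumed q of 10% to 30% and an assumed true INSTI resistance of 50%, the class-specific shift is 5 to 15 percentage points. In most of these cases sampling error at 20 to 60 failures is larger than the shift. The any-class shift is smaller, for example 3.7 points (50% − 46.3%) at s = 0.25 and q = 0.3. The documents support none of these values of q or s, so the figures show scale and are not predictions. They do not support a claim that the reported resistance will be materially wrong. The reason to act is that the study as designed holds no coded evidence that the bias is nil.

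**What to change.** 1. **Resistance Testing form (Annex 1).** For each of reverse transcriptase and integrase, add one item with three levels: sequenced with result; attempted, no result; not done. Both are copied from the laboratory report and apply to all tests the form covers, including historical and post-switch tests.
2. **AIM 3 (section 8.7).** Keep the any-class proportion. Beside it, report NNRTI and INSTI resistance separately, each over failures with a successful read of that region, and give the number without one. State the denominator of the per-mutation percentages.
3. **Feasibility step (section 8.2.1).** Ask whether the site's routine failure genotype covers both integrase and reverse transcriptase. A reader might conclude that sites answering no must be excluded. That does not follow from this point and could cost recruitment; recording the answer is enough to interpret the data.

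The cost is two form items, one feasibility question and a short addition to AIM 3. Class-specific denominators become slightly smaller and their intervals wider. No extra test or visit is asked of participants.

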#### 8.2.2. Inclusion Criteria

The study population will consist of HIV positive male or female aged 18 years or over from NEAT ID Network clinical sites who are prescribed CAB+RPV LA regimen and:

- Virologically suppressed (HIV-1 RNA <50 copies/mL) at the time of regimen initiation.
- No evidence of prior virological failure with agents of the NNRTI and INI class
- No evidence of present or past documented viral resistance to, agents of the NNRTI and INI class

#### 8.2.3 Participant Identification and Consent

The study aims to include at least 1000 people living with HIV (PLWH) across Europe, initiating CAB+RPV LA regimen. Once all relevant approvals are in place for the protocol, selected investigational sites will prospectively identify individuals initiating CAB+RPV LA regimen. Consent procedures will be undertaken as required by country specific regulations and local procedures for the collection of study data. The study participants will not need to attend any additional visits or undergo any procedures above their routine standard of care.

#### 8.3. Variables

#### 8.3.1. Exposure definitions

All new users of CAB+RPV LA regimen treated per the approved SmPC for CAB and RPV oral and LA formulations will be included in the study. The study period will include the month-long oral lead-in, followed by injectable long acting regimen use.

#### 8.3.2. Outcome definitions

**Table 1.** Regimen discontinuation: Reasons for discontinuation as tabulated below will be collected for all participants switching off CAB+RPV LA regimen.

Code	Reason for Stopping Treatment
1	Treatment failure (i.e. virological, immunological, and/or clinical failure
1.1	Virological failure
1.2	Partial virological failure (multiple blips, low level viraemia)
1.3	Immunological failure - CD4 drop (25% or more)
1.4	Clinical progression
1.5	Resistance (based on test result)
2	Abnormal fat redistribution
3	Concern of cardiovascular disease
3.1	Dyslipidaemia
3.2	Cardiovascular disease
3.3	Weight gain
4	Hypersensitivity reaction (skin eruption etc.)
5	Toxicity, predominantly from abdomen/G-I tract
5.1	Toxicity - Liver
5.2	Toxicity - Pancreas
6	Toxicity, predominantly from nervous system
6.1	Toxicity - peripheral neuropathy
6.2	Toxicity - neuropsychiatric

6.3	Toxicity - headache
7	Toxicity, predominantly from kidneys
8	Toxicity, predominantly from endocrine system
8.1	Diabetes
9	Haematological toxicity (anemia etc.)
10	Hyperlactataemia/lactic acidosis
11	Bone toxicity
12	Social contra-indication
13	Contra-indication unspecified
14	Pregnancy - toxicity concerns (during pregnancy)
15	Pregnancy - switch to a more appropriate regimen for PMTCT
16	Death
17	Toxicity, unspecified
	Availability of more effective treatment (not specifically failure or side effect
18	related)
18.1	Simplified treatment available
18.2	Treatment too complex
19	Drug interaction
19.1	Drug interaction - commencing TB/BCG treatment
20	Injection fatigue (not related to safety)
21	Injection Site Reaction
22	Non-adherence
23	Drug not available
24	Other causes, not specified above
25	Lost to follow-up
26	Defaulter
27	Individual's wish/decision, not specified above
28	Physician decision to discontinue due to confirmed low level viremia (50-200)
29	Physician's decision, not specified above
99	Unknown

#### **2.** Clinical effectiveness: assessed using the following measures:

- 1. Proportion of individuals, virologically suppressed/undetectable (<50 copies/mL) at 6,12 and 24 months following initiation of CAB+RPV LA regimen
- 2. Proportion of individuals with VL of  $<\!200$  copies/mL at 6,12 and 24 months following initiation of CAB+RPV LA regimen
- 3. Proportion of individuals with confirmed virologic failure (CVF) during the first 6 months, and at 6,12 and 24 months following initiation of CAB+RPV LA regimen defined as

- Two consecutive HIV RNA VL levels ≥200 copies/mL or
- One HIV RNA VL level \ge 200 copies/mL and regimen discontinuation within 4 months of VL \ge 200 copies/mL
- **3.** Resistance Testing: This is a non-interventional study aiming to capture SoC for PLWH in real world setting. Testing for resistance and subtype at virologic failure is part of SoC and the study will include only the clinical sites that follow the guidance for resistance testing.
  - Resistance testing along with subtype will be done for all participants with virologic failure during the 24 month follow-up period while on CAB+RPV LA
  - Resistance testing along with subtype will also be done during the 48 months following any switch from CAB+RPV LA in all participants with subsequent virologic failure on their new regimen(s) during the follow up period

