#### 8.7. Data analysis

All enrolled participants who receive at least one dose of the CAB+RPV LA regimen will be included in the analysis. Participants who are prescribed but never receive a dose of CAB+RPV LA regimen will be excluded from the analysis. Study results will be stratified by the regimen used (Q4/Monthly dosing vs Q8/Every 2 month dosing). Further, study results for co-infected patients with hepatitis B or C will be presented separately. All continuous variables will be summarized using the following descriptive statistics: n (non-missing sample size), mean, standard deviation, 1st quartile, median, 3rd quartile, maximum and minimum. The frequency and percentages (based on the non-missing sample size) of observed levels will be reported for all categorical variables. Data will be analyzed using SAS®, SPSS® or STATA®.

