## 12 Month Regimen Follow-up

Has the subject already discontinued the CAB+RPV LA regimen?	○ No ○ Yes	DIS12MO
If 'No', please complete below		
Has all relevant regimen/discontinuation data been entered for this time period?	○ No ○ Yes	REG12MO
If relevant regimen/dicontinuation data need to be recorded, please use the link below		
CAB+RPV LA Regimen Page		
Has all relevant HIV RNA Viral Load data been entered for this time period?	O No O Yes	VL12MO
If relevant HIV RNA Viral Load data need to be recorded, please use the link below		
HIV RNA Viral Load Page		
Has all relevant CD4 data been entered for this time period?	O No O Yes	CD12MO
If relevant CD4 data need to be recorded, please use the link	below	
CD4 Count Page		
Has all relevant resistance testing data been entered for this time period?	○ No ○ Yes	RES12MO
If relevant resistance testing data need to be recorded, pleas	e use the l	link below
Resistance Testing Page		
For Office Use Only		
Data Review Reason Review Da	te No	otes for Next Review
CRREAS CRDAT	L CF	RNOT

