# 12 Months Post-Switch Follow-up

Have all components of the subject's ARV regimen been recorded?	○ No ○ Yes	SWARV12MO
If relevant ARV Regimen data need to be recorded please use the link below	,	
Antiretroviral Treatment Page		
Has all relevant HIV RNA Viral Load data been entered for this time period?	○ No ○ Yes	SWVL12MO
If relevant HIV RNA Viral Load data need to be reco please use the link below	orded,	
HIV RNA Viral Load Page		
Has all relevant CD4 data been entered for this time period?	○ No ○ Yes	SWCD12MO
If relevant CD4 data need to be recorded, please us	se the link	below
CD4 Count Page		
Has all relevant resistance testing data been entered for this time period?	○ No ○ Yes	SWRES12MO
If relevant resistance testing data need to be record	ded, pleas	se use the link below
Resistance Testing Page		
For Office Use Only		
Data Review Reason F	Review Da	ate Notes for Next Review

ID	CODE	NAME	EXP.CODE	TYPE	FMT/LEN	DERIVATION	CAT. VALUES
1	20R1ID_D	Subject ID	20R1ID D	Text	10, Optional	BSL:DEMOG:SUBJID	
2		Have all components of the subject's ARV regimen b	SWARV12MO	Category	3		N=No Y=Yes
3	Hotlink			Hotlink		visit:ARI(Hirst)	
4	SWVL12MO	Has all relevant HIV RNA Viral Load data been ente	SWVL12MO	Category	3		N=No Y=Yes
5	Hotlink			Hotlink		visit:HIVRNA	
6	SWCD12MO	Has all relevant CD4 data been entered for this ti	SWCD12MO	Category	3		N=No Y=Yes
7	Hotlink			Hotlink		visit:CD4	
8	SWRES12MO	Has all relevant resistance testing dat been ente	SWRES12MO	Category	3		N=No Y=Yes
9	Hotlink			Hotlink		visit:RESTST	
Repeat	Repeating Question Group: , Borders: Yes, RowStatus: Yes, RowNumbers: Yes, DisplayRows: 3, InitialRows: 1, Min Repeats: 1, Max Repeats: 20, Main Row Type: Single-Line, Sub Row Type: Multi-Line						
10	CRREAS	Data Review Reason	CRREAS	Category	36, Optional		See Appendix
11	CRDAT	Review Date	CRDAT	Date/Time	dd/mm/yyyy, Optional		
12	CRNOT	Notes for Next Review	CRNOT	Text	500, Optional		

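### The suppression measures do not say whether a participant must still be on CAB+RPV LA or who is in the denominator, so neither available reading shows how many starters are both on the regimen and suppressed

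*Protocol*

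**What the plan says.** Section 8.3.2, under Clinical effectiveness, defines the first measure as "Proportion of individuals, virologically suppressed/undetectable (<50 copies/mL) at 6,12 and 24 months following initiation of CAB+RPV LA regimen". The second is the same with a threshold of 200 copies/mL. AIM 3 in section 8.7 repeats the first as "Proportion of participants who continue to be suppressed (VL of <50 copies/mL) at each time point", which speaks of viral load and not of regimen.

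Other parts of the protocol bear on how these measures would be computed:

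- Population (8.7): "All enrolled participants who receive at least one dose of the CAB+RPV LA regimen will be included in the analysis".
- Percentages (8.7, general convention): "The frequency and percentages (based on the non-missing sample size) of observed levels will be reported for all categorical variables".
- Follow-up after stopping (8.5): "Participants who discontinue CAB+RPV LA regimen will be followed up for 48 months after switching to another ARV regimen".
- Case report form, 12 Months Post-Switch Follow-up: it asks "Has all relevant HIV RNA Viral Load data been entered for this time period" and links to the HIV RNA Viral Load page, the same page that serves the on-regimen period.
- Case report form, 12 Month Regimen Follow-up: it asks "Has the subject already discontinued the CAB+RPV LA regimen" and is completed further only if the answer is no. The 24-month form does the same; the 6-month form has no such question.
- Censoring (AIM 3, Kaplan-Meier analysis of virologic failure only): "Follow-up will be censored at the analysis time point, or the date of last study contact, or date of discontinuation of CAB+RPV LA regimen".

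AIM 4, by contrast, sets its own population, clock and denominator for suppression after discontinuation.

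**The concern.** The suppression criterion is a viral load at a given time since initiation. Everyone dosed is in the analysis, viral loads after a switch are collected in the same form, and discontinuation is a censoring event only for time to failure. Nothing in the suppression measures themselves keeps a viral load on a later regimen from counting.

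The measures in 8.3.2 can then pull in opposite directions for one person. Someone with a single viral load of 200 or more who discontinues within four months is a confirmed virologic failure under the third measure. The same person can be suppressed at month 12 under the first, on another regimen.

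At stake is what a proportion labelled clinical effectiveness of CAB+RPV LA tells its audience, which includes health authorities. A natural question is how many who start the regimen are still on it and suppressed. Neither suppression figure answers it, and it cannot be recovered from separate failure and discontinuation proportions.

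**Working it through.** **The plan's own figures.** Section 8.4 gives exact Clopper-Pearson limits for N = 1000. Recomputed, all limits in Tables 2 and 3 agree to three decimals (failure 2%: 0.012-0.031; 6%: 0.046-0.077; discontinuation 8%: 0.064-0.099; 16%: 0.138-0.184). Half-widths are 0.92-1.52 and 1.73-2.32 points, against the stated 0.9-1.5 and 1.7-2.3. No precision is stated for suppression. By binomial symmetry, 96% suppression has the width of the 4% failure row: 0.0253, or about 1.3 points each way.

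**Inputs.**
- N = 1000 and discontinuation d = 8-16%: section 8.4, Table 3.
- s, the proportion of those on regimen with viral load below 50: assumed 98%.
- r, the proportion of stoppers below 50 on a later regimen: assumed 50%, 85% and 95%.
- No missing viral loads.

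**Formulas.**
- Any-regimen suppression, all dosed: A = (1 - d)s + d·r
- On regimen and suppressed, all dosed: B = (1 - d)s
- On-regimen observed, stoppers dropped: C = s
- Gap A - B = d·r (s cancels)
- Gap C - B = d·s

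**Results for s = 98%, r = 85%.**
- d = 8%: A = (901.6 + 68)/1000 = 97.0%; B = 901.6/1000 = 90.2%; C = 98.0%.
- d = 16%: A = (823.2 + 136)/1000 = 95.9%; B = 823.2/1000 = 82.3%; C = 98.0%.

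**Gap A - B over the assumed range of r.**

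| r (assumed) | d = 8% | d = 16% |
|---|---|---|
| 50% | 4.0 points | 8.0 points |
| 85% | 6.8 points | 13.6 points |
| 95% | 7.6 points | 15.2 points |

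The gap C - B at s = 98% is 7.8 points (d = 8%) and 15.7 points (d = 16%).

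**How a stop for failure is treated.** Take 1000 dosed, of whom 40 fail (the 4% row of Table 2), and suppose everyone else stays on and is suppressed.
- If the 40 stay on regimen and remain viraemic: 960/1000 = 96.0%.
- If the 40 stop and 85% (34) are suppressed on another regimen, the any-regimen figure is (960 + 34)/1000 = 99.4%.
- If the 40 stop and are dropped: 960/960 = 100%.
- On regimen and suppressed, over all dosed: 960/1000 = 96.0% in each case.

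So failures who stay on regimen lower both available figures, while a stop for failure does not in itself count against either.

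**The case against.** The strongest reply is that this is an omission and not an error. Denominators, handling of stoppers and missing values are commonly settled in a statistical analysis plan, which is not at hand. Suppression on any regimen is also a legitimate estimand if declared.

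Much of the protocol's structure points towards an on-regimen reading. AIM 4 treats viral loads after discontinuation separately. Section 8.5 distinguishes the 24 months of treated follow-up from the 48 months after a switch. The resistance item in 8.3.2 ties its 24-month period to being on the regimen, and the 12- and 24-month forms stop at discontinuation. A reader might infer that the protocol makes re-suppressed stoppers successes; no sentence says so. It follows only from applying the population, time origin and shared viral load form literally.

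The non-missing rule is a general descriptive convention, repeated for baseline tables. AIM 4 does not follow it, so it need not govern endpoint proportions, and it does not itself create the apparent successes.

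A reader might also infer that the suppression figure is blind to failure. It is not: failures who remain on the regimen lower it, and AIM 2 plans to tabulate them. Objective 3 names virologic failure as the effectiveness measure, suppression is one of three measures in 8.3.2, and stops are reported with coded reasons.

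All of this stands, and it limits the point. It does not remove it. The forms are data-completeness checklists, and the 6-month one has no skip. The protocol has already fixed the population, the time origin and the censoring rule for failure, so its silence on suppression leaves two readings with different results. The on-regimen reading that the structure favours still drops those who failed and left.

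**Conclusion.** The point holds as a gap in the definition with a cheap remedy. The suppression measures need an on-regimen condition and a denominator. Under either available reading, a stop for virologic failure does not count against the regimen, and the proportion of starters still on it and suppressed is not reported.

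On the any-regimen reading with no missing viral loads, the difference is 4-8 points if half of stoppers are suppressed, and about 7-15 points if 85-95% are. The smallest of these is about three times the 1.3-point half-width at 96% suppression. The stopper suppression rates are assumptions. The 8-16% is the range of a precision table and not a forecast; the trial cited in section 8.4 had 8.4% discontinuation at week 48.

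It would be tempting to call these figures bias. They are simply the discontinuation proportion times an assumed rate, and they measure the distance between two estimands. Separate reporting of failure and discontinuation mitigates the problem, so this is an improvement the sponsor should make and not a defect that invalidates the effectiveness objective.

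**What to change.** In 8.3.2 and AIM 3, state that the suppression measures use viral loads taken while on CAB+RPV LA, and that viral loads after discontinuation are used only in AIM 4.

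At each time point, report mutually exclusive categories over all dosed participants who have reached it:

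- on regimen, viral load below 50 (below 200);
- on regimen, viral load 50 or more (200 or more);
- stopped for virologic reasons;
- stopped for other reasons;
- no viral load in the window.

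State which Table 1 codes count as virologic (code 1 mixes virological, immunological and clinical failure) and where death and loss to follow-up fall, since Table 1 lists both as reasons for discontinuation. Keep the on-regimen observed proportion alongside the table; the categories add to it and do not replace it.

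The cost is wording and one extra table. Stop date, reason and dated viral loads are already in the case report form. The downside is that the all-dosed proportion is lower and mixes non-virologic stops, such as pregnancy or personal choice, with viraemia. The categories keep these apart.
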